Extensive research in animal models has shown a benefit to using intravenous (IV) vitamin C in sepsis.^{4,5} It is a cofactor for multiple enzymatic functions.⁶ In addition, one study in particular found that critically ill patients, including those with sepsis have significantly lower levels of circulating vitamin C during their acute illness than their healthy counterparts. Furthermore, the investigators found critically ill patients who were administered an infusion of vitamin C every six hours maintained normal plasma levels for the largest amount of time.⁶ One study showed that critically ill patients required up to 3 grams per day of vitamin C just to return their plasma concentrations to normal baseline levels.⁷ Additional research indicates that critically ill patients are often thiamine-deficient which is frequently missed and not treated by their clinicians.^{8,9}

Marik et al. published a novel study implicating the use of IV vitamin C, vitamin B₁, and hydrocortisone resulted in a significantly lower mortality rate for their septic patients. His team explored the utility of these medications as compared to historical controls of their previously treated septic patients.¹⁰ This study, while novel and inspiring, was designed with the acceptance of multiple confounders and potential for bias including the retrospective nature, the lack of randomization, and the lack of blinding. We propose investigating the use of IV vitamins B₁ and C in a randomized, prospective trial, eliminating the potential for selection bias.

Hypotheses

[figure not shown]
1. Primary Hypothesis: Septic patients in the ICU who receive IV vitamins B₁ and C will demonstrate a decreased mortality rate compared to septic patients who do not receive IV vitamins B₁ and C.
2. Secondary Hypotheses: Patients receiving IV vitamins B₁ and C
 - a. will have shorter hospital length of stays (HLOS)
 - b. will have shorter ICU length of stays (ICU LOS)
 - c. will demonstrate a lower 30-day readmission rate
 - d. will have fewer ventilator days
 - e. will have fewer hours on vasopressors
 - f. in addition to IV hydrocortisone for refractory septic shock will have a more profound reduction in mortality when as compared to those receiving IV vitamins B₁ and C alone

g. who also record to higher Sequential Organ Failure Assessment (SOFA) scores will have a more significant reduction in mortality than patients who record lower SOFA scores

Objectives

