The objective of this study is to determine if the administration of IV vitamins B₁ and C are effective in decreasing the mortality rates of patients with severe sepsis or septic shock. In addition, we will investigate if there are benefits to those patients who also receive hydrocortisone in an effort to explore the synergistic relationship that vitamins B₁ and C have with hydrocortisone.

Overview of Study Design

Patient Selection Criteria

1. Inclusion Criteria: Patients admitted to the ICU at Saint Francis Hospital and Medical Center who are:
 - a. Between the ages of 18 and 90 years old
 - b. Have severe sepsis or septic shock
 - i. Severe sepsis and septic shock will be defined by the Surviving Sepsis 2012 guidelines¹¹
 - c. Weight more than 30 kg
 - d. Full code
2. Exclusion Criteria: Patients
 - a. Not diagnosed with severe sepsis or septic shock
 - b. Younger than 18 or older than 90 years old
 - c. Who are pregnant
 - d. Weigh less than 30 kg

- e. Currently on hemodialysis
- f. Not located in the ICU
- g. Do not resuscitate (DNR) or do not intubate (DNI), no escalation of care, or comfort measures only (CMO)

Enrollment/Randomization

Once identified, patients who meet inclusion criteria will be approached. The majority of patients are likely to be intubated and sedated at the time of their diagnosis of severe sepsis or septic shock. In these cases, the next of kin or consenting party will be approached for each patient. The providers in the ICU, mainly physician's assistants (PAs) and residents, always contact patient's family members for consent for central lines and other invasive procedures while in the ICU. The study staff will speak to this same consenting person (in person or on the phone) and will ask them about the potential enrollment of their loved one in the study. In the absence of documentation of a healthcare proxy or conservator (as is often the case with septic patients, as it is an unexpected illness), priority will be given to the patient's spouse, followed by an adult child, followed by a parent, followed by an adult sibling. .

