The study personnel will report adverse events as soon as they become aware of them and within 24 hours of them being informed. All adverse events or unanticipated problems will be reported to the IRB. If the adverse event is thought to be related to the intervention, the medication will be stopped and the patient will be withdrawn from the study. They will be monitored closely for resolution of the adverse event. In order to ensure that the patient receives the ideal treatment for their adverse reaction and their newly-discovered allergy is documented appropriately, the research staff will un-blind the ICU staff and themselves. This will be accomplished by keeping duplicate sealed randomization envelopes. In the case of an adverse event, the research staff will open this additional envelope and inform the treating physicians.

Side Effects

Possible side effects for patients receiving IV vitamin C include diarrhea, nausea, vomiting, heartburn, headache, insomnia, and nephrolithiasis. Possible side effects for patients receiving IV vitamin B₁ include nausea, hives, wheezing, or angioedema. In the event of these reactions, the patients will be treated immediately for their allergic reaction by the primary team and will be withdrawn from the trial as previously mentioned.

Study Withdrawal

All patients who have a serious adverse event thought to be directly related to the intervention will be withdrawn from the study. The patient or their consenting proxy may revoke consent and withdraw from the study at any point as participation is completely voluntary.

Statistical Issues

The intervention arm (vitamin B₁ and C) and the control arm (sodium chloride 0.9%) will be compared statistically for demographics and patient characteristics; including age, gender, comorbidities, need for operative intervention, enteral nutrition, and Body Mass Index (BMI). Outcomes between these two groups will also be compared including hours of vasopressor use, ventilator days, HLOS, ICU LOS, comorbidities, renal function measured by patients' GFR and creatinine levels, procalcitonin levels, SOFA scores, discharge destination, readmission rates, and mortality rates. We will do a subgroup analysis of patients with septic shock as compared to those with severe sepsis. We will also do a subgroup analysis of the patients who receive hydrocortisone as opposed to those who do not.

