Fisher's exact test will be used to compare gender, operative intervention, rate of mortality and the 30-day readmission rate. Average BMI and average age will be evaluated via student's t-

test. Median number of ventilator days, average hours of vasopressor use, median daily SOFA scores, average procalcitonin levels, average creatinine levels, median GFR, median ICU LOS and median HLOS will all be compared via Mann-Whitney U test. A contingency table will be used to analyze the different types of enteral nutrition and patients' discharge destination. A multivariate regression analysis will be conducted to analyze patients' comorbidities.

Duration of Review

We will start recruiting patients on September 10, 2018. We expect recruitment and data collection to take 12 months. Data analysis and completion of a manuscript is expected to take another 12 months.

All data will be kept on a password-protected and encrypted computer located behind two locked doors. We will retain all data for three years after the completion of the study. Following this, all data will be deleted from the hard drive where they will be kept.

Publication Plan

We plan to write and submit a manuscript for publication in a peer-reviewed journal.

References

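### Vasopressor hours and ventilator days are compared by a pooled rank test that ignores support at entry: valid, but it gives up an eighth to three quarters of the power, depending on an unstated entry share

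*Combined protocol and SAP*

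**What the plan says.** Two secondary hypotheses concern time on organ support. Under Hypotheses, item 2d states that treated patients "will have fewer ventilator days" and item 2e that they "will have fewer hours on vasopressors".

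The entry criterion under Patient Selection Criteria is "Have severe sepsis or septic shock"; neither vasopressors nor mechanical ventilation is required. Enrollment/Randomization gives the only indication of the mix: "The majority of patients are likely to be intubated and sedated at the time of their diagnosis of severe sepsis or septic shock". It gives no percentage, and nothing is said about the share on vasopressors. The same section describes allocation from a single numbered list of 120, with no stratification factor.

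Statistical Issues sets the comparison as arm against arm: "Outcomes between these two groups will also be compared including hours of vasopressor use, ventilator days, HLOS, ICU LOS". It then lists "Median number of ventilator days, average hours of vasopressor use, median daily SOFA scores" among the variables tested by Mann-Whitney U. There is no restriction to patients on support, no adjustment for entry status, and no rule for patients with zero hours or days. One related analysis is planned: "We will do a subgroup analysis of patients with septic shock as compared to those with severe sepsis". Its outcomes and test are not named, and nothing comparable is planned by ventilation status.

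**The concern.** A patient who is never on vasopressors scores zero hours. If many patients are off support at entry and stay off, they form a block of tied zeros in both arms. Ranked together with everyone else, the main contrast becomes whether a patient was supported at all, and much of that was settled before randomisation. Chance differences between arms in entry status then add noise to the statistic, and a real shortening of support is harder to see.

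Entry status is known at randomisation, so this noise can be removed. At stake is the power for hypotheses 2d and 2e. The validity of the test is not in question.

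**Working it through.** **The plan's own figure.** The plan states no power, effect size or standard deviation for either duration, so there is nothing to reproduce for 2d or 2e. The 120 patients are justified on mortality of 35% versus 30%. Assuming 80% power and two-sided 5%, that contrast needs [1.96·√(2·0.325·0.675) + 0.842·√(0.35·0.65 + 0.30·0.70)]² / 0.05² ≈ 1,377 per arm, so 120 does not follow. That is a separate matter and has no bearing here.

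**Inputs.**
- From the documents: 60 per arm; whole-arm Mann-Whitney; mixed entry population; no stratification.
- Assumed: share *f* on support at entry, 0.4 to 0.9; 5% or 15% of the others start later; hours among users lognormal with log SD 1.0 and median 36 h; treatment multiplies users' hours by 0.6; two-sided 5%; deaths ignored. The median does not matter, because ranks are unchanged by rescaling.

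**Step 1: the mechanism in closed form.** Suppose everyone off support at entry stays at zero. A small treatment difference δ among supported patients becomes f²δ in the pooled comparison, because both members of a pair must be supported. The tie-corrected variance of the pooled statistic shrinks by the factor 1 − (1 − f)³. Testing supported patients alone uses a fraction f of the sample with the full δ. The relative efficiency of the pooled test is therefore

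f⁴ / [1 − (1 − f)³] ÷ f = f³ / [1 − (1 − f)³].

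- f = 0.4: 0.064/0.784 = 0.08
- f = 0.5: 0.125/0.875 = 0.14
- f = 0.7: 0.343/0.973 = 0.35
- f = 0.8: 0.512/0.992 = 0.52
- f = 0.9: 0.729/0.999 = 0.73

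The direction is fixed; the size depends heavily on f.

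**Step 2: power by simulation, with later starts allowed.** The pooled test uses the tie-corrected variance m(n − m)/12·[(n + 1) − Σ(t³ − t)/(n(n − 1))]. The van Elteren statistic is Σ(W_s − E W_s)/(n_s + 1), divided by √(Σ Var W_s/(n_s + 1)²), with two strata: on or off support at entry. Relative loss is 1 − pooled/stratified. More later starts raise pooled power and tend to lower stratified power, so the ends of the ranges are paired that way.

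| Share on vasopressors at entry | Pooled | Stratified | Relative loss |
|---|---|---|---|
| 0.4 | 8-10% | 29-32% | 1 − 10/29 = 66% to 1 − 8/32 = 75% |
| 0.5 | 13-15% | 37-41% | 1 − 15/37 = 59% to 1 − 13/41 = 68% |
| 0.6 | 18-24% | 46-52% | 1 − 24/46 = 48% to 1 − 18/52 = 65% |
| 0.7 | 27-32% | 54-60% | 1 − 32/54 = 41% to 1 − 27/60 = 55% |
| 0.8 | 41-46% | 65% | 1 − 46/65 = 29% to 1 − 41/65 = 37% |
| 0.9 | 61-62% | 71-74% | 1 − 62/71 = 13% to 1 − 61/74 = 18% |

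Monte Carlo error is about one percentage point (√(0.5·0.5/2,000) = 1.1 points), and repeat runs moved single figures by up to about four points. With no treatment effect, both tests rejected in about 4-6% of trials.

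**Step 3: where the noise comes from.** With no treatment effect, the arm difference in entry share explains about 43-80% of the variance of the pooled statistic for f from 0.4 to 0.7, 34-44% at 0.8 and 17-22% at 0.9.

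**Step 4: treatment also prevents later starts.** With later starts cut from 30% to 15% and the same 40% cut in hours, pooled versus stratified power is 41% versus 67% at f = 0.5 (loss 39%), 53% versus 71% at 0.7 (25%) and 68% versus 76% at 0.9 (11%). With later starts at 15% and halved, it is 22% versus 56% at f = 0.5 (61%). The loss is thus clearly smaller when later starts are common and treatment prevents many of them. The stratified test was ahead in every setting run.

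**Step 5: ventilator days.** These were not simulated separately. The table carries over only if the spread, effect and later-start rate are similar, and whole days add ties among users. An intubated majority rules out f = 0.4 and is compatible with 0.8 or 0.9.

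**The case against.** The strongest reply is that the size rests on a share the plan never gives. A reader might infer that 2d and 2e lose most of their power. That holds only if about 60% or fewer are on support at entry and treatment acts mainly on duration. At 0.8 the loss is about a third, and at 0.9 under a fifth. For ventilator days the plan's own expectation of an intubated majority points away from the worst case. This objection stands, and it is why the size is given as a range.

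A second reply is that 2d and 2e speak of fewer days and hours over all patients, which includes never starting support, so a whole-arm comparison matches the hypotheses. That is fair, but a van Elteren test also uses every patient and picks up prevented starts within the off-support stratum. It was still the more powerful test in Step 4.

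A third is that the shock versus severe sepsis subgroup already covers the matter. It may recover part of the loss for vasopressor hours, since shock and vasopressor use are closely linked. However, it is tied to no outcome or test, yields no single combined test of 2e, and does not address ventilation.

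Finally, the power figures ignore deaths although the plan cites 35% mortality. They compare two tests under stated assumptions and are not forecasts of the trial's power.

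**Conclusion.** The point holds as one of efficiency. The planned test is valid under the null because allocation is random, but it leaves unused a baseline fact that accounts for an appreciable part of its noise. Under the assumptions above, the loss for vasopressor hours runs from about an eighth of the stratified test's power (share 0.9) to about three quarters (share 0.4). It is smaller where later starts are common and treatment prevents many of them. For ventilator days it probably lies towards the smaller end if a large majority are intubated at entry.

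Two stronger readings are not supported. One is that the pooled test mainly measures chance imbalance: that depends on the share, the proportion of variance falls to about a fifth at 0.9, and the error rate stays near 5% throughout. The other is that the pooled test is what would make a null result uninformative: the stratified test itself reaches only 29-74% in these settings, so 120 patients would leave a null result weak either way.

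**What to change.** In Statistical Issues, before unblinding:

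- Replace the pooled Mann-Whitney test for vasopressor hours with a van Elteren (stratified Wilcoxon) test stratified by vasopressor use at randomisation (yes/no).
- Do the same for ventilator days, stratified by mechanical ventilation at randomisation (yes/no).
- Report each duration by arm within those strata, together with the proportion of patients off support at entry who later start it.

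The cost is a few sentences in the analysis plan and two yes/no entry fields that should be obtainable from the chart. No extra patients or procedures are needed. Timing matters: a stratified test introduced after a null pooled result would carry little weight.

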Data will be kept on an encrypted, password-protected computer behind two locked doors. Data will be managed by the investigators who will each have their own login.

Study Workflow

Patients admitted to the ICU who have severe sepsis or septic shock will be identified by the nursing staff, PAs, or physicians caring for them. These patients' consenting party will be approached within 24 hours of their presentation to the ED in an attempt to obtain informed consent. Following consent, the pharmacy will be notified of the study patient, randomization will occur, and the mixed medications (control or intervention) will be delivered to the patient's bedside in the ICU. Consented patients will receive 1.5g of vitamin C in 100mL of 0.9% sodium chloride (normal saline) every six hours for four days or until discharge from the ICU, whichever happens first (seventeen dose maximum). In addition, they will receive 200 mg IV vitamin B₁ every 12 hours in 100 mL of normal saline for four days or until ICU discharge (whichever happens first, nine dose maximum). Patients in the control arm will receive the 100 mL of 0.9% sodium chloride every six hours and 100 mL of 0.9% sodium chloride every 12 hours to act as placebos for the vitamin C and B₁ respectively. Doses up to 200 mg/kg/day were found to be safe in humans in one study.⁶ Several studies have been conducted in human subjects using IV vitamin B₁ and C, often at higher doses than proposed here, and have not seen serious side effects.^{10,12-14}

Some patients may receive hydrocortisone IV for refractory septic shock outside of this study protocol. This will be at the discretion of the treating physician and will not be included in the randomized and blinded intervention. Hydrocortisone has been shown in some studies to help

in patients with refractory septic shock.^{15,16} However, it is not uniformly employed. Patients receiving hydrocortisone will undergo a subgroup analysis to better elucidate the synergistic effects of hydrocortisone with vitamins B₁ and C.

After discharge, patients will be followed for 30 days to track hospital readmissions.

Reporting of Adverse Events

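### The SOFA outcome has no fixed window and no rule for death or ICU discharge, so it can miss faster organ recovery and a null result would be hard to interpret

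*Combined protocol and SAP*

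**What the plan says.** The Statistical Issues section lists the outcomes to be compared between arms, among them "procalcitonin levels, SOFA scores, discharge destination, readmission rates, and mortality rates". The test paragraph of that section names the SOFA summary as "median daily SOFA scores, average procalcitonin levels" and ends its list with "median ICU LOS and median HLOS will all be compared via Mann-Whitney U test". Nothing more is said about SOFA as an outcome: no assessment days, no window, no unit of summary, and no rule for patients who die or leave the ICU.

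Two statements in Study Workflow bear on when scores would exist. Vitamin C is given "every six hours for four days or until discharge from the ICU, whichever happens first"; this concerns dosing and is not stated to be the SOFA window. Follow-up beyond the stay is described in one sentence: "After discharge, patients will be followed for 30 days to track hospital readmissions".

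In the Hypotheses section SOFA appears only as an effect modifier, in secondary hypothesis 2g: patients "who also record to higher Sequential Organ Failure Assessment (SOFA) scores will have a more significant reduction in mortality" than those with lower scores.

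**The concern.** Daily scores can be collected only while a patient is alive and under observation. Since the only follow-up described after discharge is for readmissions, the natural inference is that scoring ends at discharge or death. The number of scores per patient then depends on the outcome: patients who recover quickly contribute few, and so do patients who die early.

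This matters under either meaning of the phrase. A within-patient median over the stay describes the middle of the patient's course and not how long the course took. A patient who dies on day 1 contributes very few scores and carries no penalty for dying. An arm median on each day compares, on later days, the patients left after the quickest recoveries and the early deaths have gone. Adjusting for the entry score would cure neither problem.

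SOFA is the only multi-organ score among the listed outcomes. If the vitamins speed organ recovery, a null result on this summary could be misread as no effect on organ dysfunction.

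**Working it through.** **Plan's own figure.** None is given for SOFA. The stated sample size (120, 60 per arm) is tied to mortality of 35% versus 30% and is used here only for the number per arm.

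**Step 1: time compression (no simulation needed).** Let a survivor's score on day t of a stay of L days be f(t/L), falling from S0 at entry to Sd at discharge. With evenly spaced scores the whole-stay median is f(1/2), which does not contain L. Take S0 = 10, Sd = 2 and stays of 8 versus 4 days:

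- linear fall: (10 + 2)/2 = 6.0 in both
- exponential fall: √(10 × 2) = 4.47 in both
- level for half the stay, then linear: 10 in both

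A direct example: 9, 6, 3 (two days) and 9, 8, 7, 6, 5, 4, 3 (six days) both have median 6.

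If the course is not purely compressed, the median can move either way:

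- Fixed two-day lag before improvement, then 1 or 2 points a day: 10,10,10,9,8,7,6,5,4,3,2 has median 7, and 10,10,10,8,6,4,2 has median 8. The faster patient looks worse.
- Two further days scored at 2 after the linear fall: median 5 for the 8-day course and 4 for the 4-day course. The faster patient looks slightly better.

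A fixed day separates the linear courses: the day-3 scores are 7 and 4.

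**Step 2: power, 60 per arm, two-sided 5% Mann-Whitney, recovery twice as fast on treatment.** No SOFA input below is in the documents; all are assumptions.

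- *Set A:* entry SOFA mean 9 (SD 3); survivors fall about 1 point a day (log SD 0.5); discharge at SOFA 3; daily noise SD 1; mortality (35 + 30)/2 = 32.5% in both arms. The fixed-day score gives death 24 and carries the last ICU score forward. Where extra days are scored, scores fall to a floor of about 1.5.
- *Set B:* entry mean 9 (SD 3); discharge at SOFA 1-3; log-normal stay with median 8 days; scores rising before death; mortality 35% in both arms. Death scores 24 and discharge scores 2.

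| Scoring | Whole-stay median | Observed patients only | Fixed-day score |
|---|---|---|---|
| A, stops at recovery | 5-7% | 9% (day 4) | 44-51% |
| A, 1-2 further days | 20-32% | 35-61% (days 2 and 4) | 46-55% |
| A, at least 5 scored days | 25% | not run | 48% |
| A, at least 7 scored days | 41% | not run | 49% |
| B, stops at recovery | 3.5% | 10% (day 4) | 62% |

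With recovery 1.5 times as fast and scoring that stops at recovery, the whole-stay median rejects in 4.4% (A) and 4.8% (B) of trials, against 19.9% and 27.2% for the fixed-day score. With no effect at all, every version rejects about 5% of the time. The problem is sensitivity and interpretation, not false positives.

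**Step 3: what selective exit does to the day-by-day reading.** In Set B the typical day-4 arm medians are 6.94 versus 4.15 when deaths and discharges are scored, a difference of 2.79. Among patients still observed they are 6.26 versus 5.58, a difference of 0.68.

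**Step 4: a mortality effect alone (Set B).** At 35% versus 30% mortality the whole-stay median rejects in 10% of trials and the fixed-day score in 9.2%. At 35% versus 10% the figures are 57% and 60%. The fixed day gains on recovery speed and adds almost nothing for mortality.

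**The case against.** A reader might infer that this outcome can barely register the effect the trial looks for, so that a null result is close to guaranteed. The documents do not support that, for three reasons.

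1. *The reading is not stated.* The other medians in the same sentence, such as length of stay, summarise across patients with one value each. Read in parallel, the phrase is the arm median on each day. The exact invariance in Step 1 then does not apply, and early days keep useful power: 34% on day 2 under Set A even with discharge at recovery.
2. *The stopping point is inferred.* No sentence says SOFA scoring ends at recovery. One or two further scored days lift the whole-stay median from 5-7% to 20-32%.
3. *The effect sought is mainly another one.* The primary hypothesis is that treated patients "will demonstrate a decreased mortality rate compared to septic patients who do not receive IV vitamins B₁ and C". Recovery speed has its own listed outcomes: ICU and hospital stay, ventilator days and vasopressor hours. In Set B length of stay among survivors detects twice-as-fast recovery in about 100% of trials.

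All three points stand against the strong claim. They do not remove the defect. On the day-by-day reading, later days still compare selected patients. Length of stay does not measure organ dysfunction, and the near-100% figure is for survivors only, a restriction the plan does not make. In every twice-as-fast scenario where the two were compared, the fixed-day score beat the whole-stay median, though by 7 to 10 days of scoring the margin would be expected to be small (already 49% versus 41% at a minimum of 7 days).

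It is also fair to say that ranking death worst turns the outcome into a composite of death and organ dysfunction, which is a different quantity from SOFA alone.

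**Conclusion.** The concern holds in a limited form. The SOFA summary is undefined as to window, unit, and handling of death and discharge. On the whole-stay reading it is largely insensitive to recovery speed; on the day-by-day reading its later comparisons are distorted by selective exit, most severely when discharge promptly follows recovery.

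The invariance under time compression is exact and needs no assumed SOFA values. The power figures rest wholly on assumed scores, discharge rules and death patterns and should be read as a range: about 5-7% to 20-30% for the whole-stay median, against about 45-50% for a fixed-day score under Set A.

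The consequence is confined to one unranked outcome with no outcome hypothesis of its own. The mortality conclusion is untouched. What is lost is the ability to read a null SOFA result as evidence of no effect on organ dysfunction.

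**What to change.** In the Statistical Issues section, define the SOFA outcome as the score at one fixed time from randomisation, for example 96 hours, which matches the planned four-day course. Include every randomised patient. Anchoring on randomisation rather than first dose gives a time point to patients who are randomised but never treated. Rank death before that time worst, carry the last ICU score forward for patients discharged earlier, and keep the planned Mann-Whitney test. State that the result is a composite of death and organ dysfunction, and report survivors only as a sensitivity analysis. Keep the daily medians by arm as a descriptive plot, with the number of patients observed on each day.

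The cost is a change of wording before unblinding, since daily scores are already implied by the plan. The downsides are that the rank given to death is a convention, that deaths add mortality noise to the comparison, and that carrying forward the last ICU score assumes no change after discharge.

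### SOFA, procalcitonin, creatinine and GFR are compared by an unadjusted rank test with no pre-treatment value and no fixed day: a valid test, but one that gives up precision and leaves each comparison open to chance baseline imbalance

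*Combined protocol and SAP*

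**What the plan says.** Statistical Issues lists the between-arm outcomes, among them "renal function measured by patients' GFR and creatinine levels, procalcitonin levels, SOFA scores, discharge destination, readmission rates, and mortality rates". The next paragraph of that section gives the method. The variables named there include "median daily SOFA scores" and "average procalcitonin levels, average creatinine levels, median GFR", and the sentence ends "median ICU LOS and median HLOS will all be compared via Mann-Whitney U test".

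For these four measures the documents define no baseline value, change score, measurement day or repeated-measures model. The one regression in the plan is described in full as follows: "A multivariate regression analysis will be conducted to analyze patients' comorbidities". It names no outcome and no covariates. The patient characteristics listed for comparison between arms are age, gender, comorbidities, operative intervention, enteral nutrition and BMI, so none of the four measures is on that list.

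The Hypotheses section does not name any of the four as an outcome. SOFA appears there only as a possible modifier of the mortality effect.

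**The concern.** A patient's organ-failure score, renal function or procalcitonin a few days into treatment can be expected to depend partly on its level at entry. A comparison that ignores the entry level treats that predictable variation as noise. With 60 patients per arm, the arms may also differ at entry by chance, and an unadjusted comparison carries part of that difference into the result.

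Without a named day, it is also unclear which value enters the test. Nothing says that it must be post-dose, or that it must fall inside the treatment window.

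At stake is how much the trial can say about organ function and inflammation, and how far a difference in these measures can be read as an effect of treatment.

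**Working it through.** **Inputs.** Enrollment/Randomization gives 60 patients per arm. The plan states no power, effect size, SD or correlation for these four measures, so there is no figure of its own to reproduce. The following are therefore assumptions: a correlation r of 0.3, 0.5 or 0.7 between the pre-dose and post-dose values, an effect of 0.4 SD, roughly normal data (after a log transformation where needed), and two-sided alpha of 0.05.

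**Step 1: variance.** Adjusting for baseline multiplies the variance of the arm difference by 1 − r².

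- r = 0.3: 1 − 0.09 = 0.91, a 9% reduction
- r = 0.5: 1 − 0.25 = 0.75, a 25% reduction
- r = 0.7: 1 − 0.49 = 0.51, a 49% reduction

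Equivalently, an adjusted analysis would match the unadjusted precision of 120 patients with 120 × (1 − r²), or about 109, 90 or 61 patients.

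**Step 2: power.** This uses a two-sample t-test with 60 per arm and standardised effect 0.4/√(1 − r²).

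| r | Standardised effect | Power |
|---|---|---|
| unadjusted | 0.400 | 58.4% |
| 0.3 | 0.419 | 62.5% |
| 0.5 | 0.462 | 70.9% |
| 0.7 | 0.560 | 86.1% |

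The difference detectable with 80% power is (1.96 + 0.84) × √(2/60) = 0.51 SD unadjusted. Multiplying by √(1 − r²) gives 0.49, 0.44 or 0.37 SD.

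**Step 3: the same check with the planned test.** Step 2 uses a t-test, so Mann-Whitney on the follow-up value was simulated against ANCOVA (5,000 trials per setting, normal data, 60 per arm).

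| r | Power at 0.4 SD, Mann-Whitney | Power at 0.4 SD, ANCOVA | Type I error, Mann-Whitney, all trials |
|---|---|---|---|
| 0.3 | 56% | 61% | 4.6% |
| 0.5 | 56% | 71% | 4.7% |
| 0.7 | 57% | 86% | 5.2% |

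**Step 4: chance imbalance.** The standard error of a baseline difference is √(2/60) = 0.183 SD, so a difference beyond 1.96 × 0.183 = 0.36 SD arises in about 5% of trials for each measure. The expected carry-over to follow-up is r times the imbalance. For 0.36 SD that is 0.11, 0.18 or 0.25 SD. Among simulated trials with an imbalance that large and no treatment effect, Mann-Whitney rejected in 9.6%, 14.5% and 30.9% (r = 0.3, 0.5, 0.7), and ANCOVA in 3.0%, 4.7% and 3.5%. Each of these percentages rests on roughly 250 trials (5% of 5,000), so the Mann-Whitney figures are uncertain by about 2 to 3 percentage points (one standard error).

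**The case against.** The best defence is that the planned test is sound. The arms are randomised, the test keeps its 5% level, and a rank test suits skewed procalcitonin and ordinal SOFA. All of that stands. A reader might infer from the conditional rates in Step 4 that the plan inflates false positives. It does not: those rates apply only to the roughly 5% of trials with a large imbalance, and the overall rate stays near 5%. The carry-over is also partial, not one for one.

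A reader might also infer that each patient's values are averaged over the stay, with the pre-dose value included and long-stay patients weighted more heavily. The text does not establish this. The same paragraph speaks of average age and median length of stay, where the adjective can only describe the group summary. Only SOFA is called daily, and "median daily SOFA scores" could mean a separate test for each day. Even if values were averaged within patient, each patient would enter the rank test once, with equal weight. What remains is that no day is named and baseline is not used under any of these readings.

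The gain depends on a correlation that the documents do not give, and at r = 0.3 it is small. The formula describes a single follow-up value on a normal scale, so it is only a guide for skewed or ordinal measures. Finally, none of the four is a hypothesised outcome. Vasopressor hours and ventilator days are the organ-support outcomes that the plan does hypothesise, so these four should not be called the trial's main evidence on organ function.

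**Conclusion.** The point holds as a matter of efficiency and specification. As written, the four measures are compared without their pre-treatment values and without a fixed day. For assumed correlations of 0.3 to 0.7, that forgoes a variance reduction of 9% to 49%. For a 0.4 SD effect with 60 per arm, power is about 58% where it could be about 62% to 86%. The direction holds for any appreciable correlation; the size rests on the assumed correlation, effect and normal scale.

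The documents do not support a claim of an invalid test, an inflated overall error rate, or averages contaminated by pre-dose values. The primary mortality comparison by Fisher's exact test is untouched. The change is worth making because it is cheap, but its priority is that of supporting outcomes.

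**What to change.** In Statistical Issues, for each of SOFA, procalcitonin, creatinine and GFR:

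1. Define baseline as the last value before the first dose, and exclude it from the outcome.
2. Name one post-dose day within the four-day treatment window and compare the arms on that day's value by ANCOVA adjusted for baseline. Use a log scale for procalcitonin and creatinine, or a rank-based ANCOVA.
3. Report the adjusted difference with its 95% CI.
4. Use a repeated-measures model with baseline, day and arm only where daily values are collected. The documents describe only SOFA as daily.
5. State how values cut short by death or ICU discharge are handled. With 30% to 35% mortality expected and dosing ending at ICU discharge, treating such values as simply missing at random would need justification. A worst-rank analysis for deaths is one possible sensitivity analysis.
6. Keep the planned Mann-Whitney test on the post-dose value as a further sensitivity analysis. A change score is a poorer choice: its variance is 2(1 − r) times that of the follow-up value, which is 1.4 times at r = 0.3, and it does worse than follow-up alone whenever r is below 0.5.

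The cost is SAP wording, modest extra analysis and some reliance on a model. No new data are needed if a pre-dose value and a value on the named day are already recorded. The documents do not give a collection schedule for procalcitonin, creatinine or GFR, so this should be confirmed first. The change should be made before unblinding.
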